1 INTRODUCTION

1.1 STUDY OBJECTIVES

1.1.1 Primary Objective

- Determine the efficacy with respect to objective response rate of olaparib in patients with malignant mesothelioma based on somatic or germline mutation status of DNA repair genes
- 1.1.2 Secondary Objectives
 - To assess the safety and tolerability of olaparib in patients with mesothelioma
 - To assess progression free survival in patients with mesothelioma treated with olaparib monotherapy
 - To investigate the potential of soluble mesothelin levels and levels of megakaryocyte potentiating factor to predict any therapeutic response

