6.3.2 Genomic Data Sharing Plan

Unlinked genomic data will be deposited in public genomic databases such as dbGaP in compliance with the NIH Genomic Data Sharing Policy.

6.4 **Response Criteria**

For the purposes of this study, patients should be re-evaluated for response every 6 weeks (2 cycles). In addition to a baseline scan, confirmatory scans should also be obtained no less than 4 weeks following initial documentation of objective response.

Response and progression will be assessed by the investigator on the basis of physical examinations, computed tomography (CT) or Magnetic Resonance (MR) scans, and potentially other modalities according to standard of care.

For peritoneal mesothelioma, the international criteria proposed by the revised Response Evaluation Criteria in Solid Tumors (RECIST) guideline (version 1.1)^[17] will be used. Changes in

the largest diameter (unidimensional measurement) of the tumor lesions and the shortest diameter in the case of malignant lymph nodes are used in the RECIST criteria.

For pleural mesothelioma, modified RECIST for MPM (malignant pleural mesothelioma)^[18] should be used as described in section 6.4.2.

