6.4.4 Progression-Free Survival

Progression free survival (PFS) is defined as the duration of time from start of treatment to time of progression or death, whichever occurs first. Patients that have not progressed or died will be censored at the date of the last tumor assessment.

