10.1.2 Secondary Endpoints

Secondary objectives include: determining safety and tolerability of olaparib in patients with mesothelioma; estimation of progression free-survival (PFS), identifying biomarkers of response to olaparib, and evaluating serum mesothelin and MPF as biomarkers of anti-tumor efficacy.

| Objective | Endpoints | | |
|---|---|--|--|
| Assess safety and tolerability | • Numbers of DLTs identified by type and grade – assessed approximately 21 days after enrollment of last subject. | | |
| Assess PFS | Kaplan Meier analysis of progression free survival in all patients combined – assessed approximately 6 months after enrollment of last subject depending on outcomes noted. | | |
| Investigate potential soluble mesothelin levels and MPF | Comparison of responders vs. non-responders with respect to biomarker baseline level changes over time – assessed approximately 6 months after enrollment of last subject depending on outcomes noted. Preliminary evaluation of mesothelin and MPF with respect to objective response – assessed approximately 6 months after enrollment of last subject depending on outcomes noted. | | |

| Objective | Endpoints |
|-----------|--|
| | • Preliminary evaluation of mesothelin and MPF with respect to progression free survival – assessed approximately 6 months after enrollment of last subject depending on outcomes noted. |

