10.2 SAMPLE SIZE DETERMINATION

The primary objective of this pilot study is to obtain preliminary estimates of the overall response rates to olaparib in patients with malignant mesothelioma according to their individual comparison group:

- Comparison Group 1 Patients with a germline mutation in DNA repair genes (estimated at 10-12% of all patients)
- Comparison Group 2 Patients with *BAP1* somatic mutations (estimated at 50-60% of all patients)
- Comparison Group 3 Patients with neither germline DNA repair mutations nor BAP1 somatic mutations (estimated at 30-40% of all patients).

All patients will be enrolled without consideration of their mutation status, and then the results will be retrospectively categorized and evaluated by mutation type. These results will be used to determine if there are any further patients to be enrolled following an amendment taking into consideration the preliminary results obtained.

It would be desirable if overall there was at least approximately a 20% response rate. The study will initially plan to enroll 30 evaluable patients in order to estimate the overall response rate with a maximum two-sided 90% confidence interval width of +/- 16%. If the observed response rate were 15-20%, the confidence interval width overall would be approximately +/-10-15%. Thus, 30 patients are adequate for an overall assessment of response. If during the initial 20 patients evaluated, there are 0-1 responses noted, then no further patients will be enrolled as soon as this can be determined since the upper one-sided 90% confidence interval bound on 1/20 is 18.1%, which is below the approximate response rate of interest. Because accrual is proceeding rapidly on the study and continued enrollment is desirable at this time, up to 25 total patients may be enrolled (5 additional patients) while awaiting the response evaluations among the first 20 patients.

It is expected that 30 evaluable patients can be enrolled in approximately 12-18 months. As patient non-compliance with study drug dosing will prevent them from being evaluable, the accrual ceiling must be adjusted accordingly. Estimating an average of 3 cycles of study therapy and a non-compliance rate of 10% per cycle the accrual ceiling will be set at 40 patients.

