10.4.3 Analysis of the Secondary Endpoint(s)

The secondary objectives will be assessed using the following measures.

Descriptive tabulations of toxicity will be provided.

Kaplan-Meier analysis of PFS will be performed, including reporting PFS at relevant time points, along with 95% confidence intervals.

Responders vs. non-responders will be compared with respect to serum mesothelin and MPF baseline levels or changes over time (see section 5.1 for biomarkers to be reported), with results compared between response categories using two-tailed Wilcoxon rank sum tests.

Serum mesothelin and MPF at baseline will be categorized into two groups of approximately equal size and tested for their association with PFS using Kaplan-Meier curves and two-tailed log-rank tests. Changes in serum mesothelin and MPF will be determined up until the end of treatment, and landmark analyses will be used to assess their association with PFS.

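### Optional: test baseline mesothelin and MPF against PFS as continuous log markers. For a graded effect and a roughly normal log marker, the planned two-group split makes 30 patients count as about 19-20.

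*Combined protocol and SAP*

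**What the plan says.** Section 10.4.3 sets out three kinds of marker analysis.

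- **Baseline level against PFS:** "Serum mesothelin and MPF at baseline will be categorized into two groups of approximately equal size and tested for their association with PFS". The comparison is a two-sided log-rank test, displayed with Kaplan-Meier curves.
- **Baseline level or change against response:** responders and non-responders are compared, "with results compared between response categories using two-tailed Wilcoxon rank sum tests". The markers are not split here.
- **Change during treatment against PFS:** landmark analyses.

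The first serves an endpoint listed in Section 10.1.2: "Preliminary evaluation of mesothelin and MPF with respect to progression free survival". The marker objective in Section 1.1.2 is worded in terms of response: "To investigate the potential of soluble mesothelin levels and levels of megakaryocyte potentiating factor to predict any therapeutic response". Section 10.4.9 plans no exploratory analyses, so baseline level is never tested against PFS with the marker unsplit. The plan gives no alpha, effect size, power or event count for this test.

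**The concern.** A median split treats a patient just above the median like the patient with the highest value. If risk changes steadily along the marker scale, the ordering within each half carries information that the log-rank test does not use. About 30 patients leave little to spare, so a moderate or strong graded association is more likely to be missed than it need be.

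The stakes are modest. The stated marker objective is response, and that test is unsplit. It may be thin, though. At the 20% response rate that Section 10.2 calls desirable, 30 patients give 0.20 × 30 = 6 responders. Sections 10.2 and 10.4.6 also provide for stopping on 0-1 responses among the first 20. With no responder the Wilcoxon test cannot be run. With one, its smallest exact two-sided p-value is 2/20 = 0.10 at n = 20 and 2/25 = 0.08 at n = 25. In those outcomes the PFS analyses would carry the marker question.

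**Working it through.** **Inputs from the plan.** Size and accrual: "It is expected that 30 evaluable patients can be enrolled in approximately 12-18 months" (Section 10.2), taken as n = 30 with uniform accrual over 52 or 78 weeks. Scans: "patients should be re-evaluated for response every 6 weeks (2 cycles" (Section 6.4). Cut-off: about 6 months after the last enrolment (Section 10.1.2), taken as 26 weeks. Censoring: "Patients that have not progressed or died will be censored at the date of the last tumor assessment" (Section 6.4.4).

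**Assumed, because the plan does not say.** Two-sided 5% level; exponential PFS with hazard proportional to exp(b·x), where x is the standardised log marker and b = ln(HR per SD); median PFS 12, 18 or 26 weeks; progression dated to the next 6-week scan.

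**The plan's own figure.** There is none for this test. The basis for n = 30 does reproduce: the exact 90% interval for 15/30 is 33.9% to 66.1%, a half-width of 16.1 points against the stated 16%.

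**Step 1: information kept.** For a log-linear effect, the relative efficiency of the split is the squared correlation between the marker and its median split:

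efficiency = (E|X − median|)² / Var(X)

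For a normal log marker, E|X| = √(2/π) with unit variance, so efficiency = 2/π = 0.637 and 30 × 0.637 = 19.1 patients.

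| Distribution of log marker | Efficiency | Equivalent unsplit patients out of 30 |
|---|---|---|
| Uniform | 0.750 | 22.5 |
| Normal | 0.637 | 19.1 |
| Logistic | 0.584 | 17.5 |
| Double-exponential | 0.500 | 15.0 |
| Exponential | 0.480 | 14.4 |

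At the early-stop sizes, a normal marker gives 20 × 0.637 = 12.7 and 25 × 0.637 = 15.9.

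**Step 2: power for a graded effect.** 6,000 simulated trials per scenario, normal log marker, 21-28 expected events. The log-rank test on the sample-median split is compared with the Cox score test on x. Ranges cover the three medians and both accrual periods.

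| HR per SD | Split | Continuous |
|---|---|---|
| 1.0 (type I error) | 5.3-5.8% | 5.1-5.8% |
| 1.25 | 12-15% | 16-20% |
| 1.5 | 28-33% | 41-48% |
| 2.0 | 59-68% | 80-87% |

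The gain does not come from a higher false-positive rate. Under all five distributions in Step 1 (median 18 weeks, 65-week accrual), the continuous test had more power at HR 1.5 and at HR 2.0. The gap was smallest for the uniform (37% versus 48% at HR 1.5; 72% versus 88% at HR 2.0).

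**Step 3: does 19-20 hold in simulation?** With median 12 weeks and 52-week accrual, the split at n = 30 had power 0.322 (HR 1.5) and 0.664 (HR 2.0). The continuous test had 0.312 and 0.666 at n = 19, and 0.336 and 0.688 at n = 20. A simpler simulation without scan dating, at b = 0.3, 0.5 and 0.7, matched the split at n = 30 to a continuous test at about n = 19-21.

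**Step 4: the reverse case, a step effect.** Step HR of 3, 65-week accrual, median 12-18 weeks:

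| Where the step lies | Split | Continuous |
|---|---|---|
| Exactly at the sample median | 78-79% | 53-54% |
| Population median | 61-62% | 51-53% |
| 60th percentile | 47-49% | 44-46% |
| 75th percentile | 21-22% | 27-31% |

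**The case against.** The strongest reply is that this is a preference. The trial is a pilot sized for response rate, and the endpoint is described as preliminary. No power is promised for it, and a two-group Kaplan-Meier display is easy to read at this size. All of that stands, which is why the point is optional.

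The second reply is that the figures rest on a marker distribution and an effect shape that the plan does not give. This also stands, and the 14.4-22.5 range is not a bound. A t distribution with 3 degrees of freedom gives 12.2, and an effect linear in a raw log-normal marker (log SD 1) gives 8.1. In the other direction, an equal mixture of two normals centred at ±2 or ±3 within-component SDs keeps 81% or 90% of the information, or 24.4 or 27.0 patients. The eligible population mixes disease sites and histologic subtypes, so a two-peaked marker cannot be excluded.

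The third reply is that the change is a trade-off. If the truth is a step at the median, the split is better by about 10 points (population median) to 25 points (sample median). The documents do not show which shape is likelier. They do not argue for a threshold at the median either, since the cut is defined by group size.

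Finally, the gain is limited. At HR 1.25 both tests are weak, and at HR 1.5 the continuous test still misses more than half the time. It reaches 80% only at HR 2.0 per SD. For a normal marker the two halves' means differ by 2√(2/π) = 1.60 SD, so this is a hazard ratio of about 2^1.60 ≈ 3 between the average high-half and low-half patient.

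These points bear on how much weight the finding deserves. They do not change the arithmetic, or the fact that baseline level is never tested unsplit against PFS.

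**Conclusion.** The point holds as an optional improvement. The planned test is valid, the split is not chosen by outcome, and no stated figure is contradicted. Under a graded log-linear effect and a roughly normal log marker, splitting costs about 36% of the information. That is a loss of roughly 13-15 percentage points of power at HR 1.5 per SD and about 20 at HR 2.0. Under a step near the median the advantage reverses. The result rests on the assumed effect shape, marker distribution, 5% level and PFS medians, and on reaching 30 patients. It affects one secondary analysis, and no decision in the plan depends on it.

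**What to change.** In Section 10.4.3, make the baseline test a Cox model for PFS with the log-transformed marker as a single continuous covariate, using a score or likelihood-ratio test, separately for mesothelin and MPF. Keep the two-group Kaplan-Meier curves and the log-rank result as a supporting display, so that nothing now planned is lost and a step near the median would still be visible. Settle the wording before marker and PFS data are looked at together.

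The cost is SAP wording only, with no new samples, visits or patients. The price is some power if the true effect is a step near the median, because the Cox test assumes a roughly log-linear effect.

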10.4.4 Safety Analyses

Safety of the agent will be assessed by reporting the grade of adverse events noted in each patient and reporting the proportion with grade 3 and grade 4 adverse events. Safety data will be presented

in individual listings. Summaries will also be prepared. The safety data will consist of the reporting of all adverse events, vital signs, physical examination data, and appropriate laboratory safety data.

10.4.5 Baseline Descriptive Statistics

Limited demographic and clinical characteristics of all patients will be reported.

10.4.6 Planned Interim Analyses

If during the initial 20 patients evaluated, there are 0-1 responses noted, then no further patients will be enrolled as soon as this can be determined. since the upper one-sided 90% confidence interval bound on 1/20 is 18.1%, which is below the approximate response rate of interest. Because accrual is proceeding rapidly on the study and continued enrollment is desirable at this time, up to 25 total patients may be enrolled (5 additional patients) while awaiting the response evaluations among the first 20 patients.

10.4.7 Sub-Group Analyses

None will be performed.

10.4.8 Tabulation of Individual Participant Data

Toxicity data may be reported on a per-patient basis if adequate events are noted, or may be summarized.

10.4.9 Exploratory Analyses

No exploratory analyses are planned.

11 COLLABORATIVE AGREEMENTS

11.1 COLLABORATIVE RESEARCH AND DEVELOPMENT AGREEMENT (CRADA)

The study agent, olaparib, will be provided under a CRADA (# 02299) between NCI and the manufacturer, AstraZeneca.

11.2 INTRAMURAL MATERIAL TRANSFER AGREEMENT (IMTA)

Rather than amending the above mentioned CRADA to include the current study, an internal MTA (#43420-27) was executed to make the study agent supplied under the CRADA available for the current study.

11.3 QUALITY AGREEMENT

As a supplement to address items required by the sponsor that were not addressed in the CRADA or the MTA, a quality agreement was executed between the [name]. and AstraZeneca to establish the obligations and the responsibilities of each party relating to the quality assurance requirements of the manufacture, analysis, packing and/or release by AstraZeneca of products and the supply to the investigator.

12 HUMAN SUBJECTS PROTECTIONS

12.1 RATIONALE FOR SUBJECT SELECTION

This study will be open to all individuals with malignant mesothelioma regardless of gender, ethnicity, or race provided that the aforementioned inclusion and exclusion criteria are met. The selection criteria reflect all available nonclinical and clinical safety experience with olaparib. Further, the selection criteria address the potential pharmacokinetics issues that may confound the reliable assessment of the study objective related to the pharmacokinetic drug-drug interaction.

The treatment of men as well as women is justified because of the severity of the underlying neoplastic disease. Men and women who use appropriate contraception or women who are not of child-bearing potential will be enrolled into this study. The proportion of men and women enrolled into the dose-escalation cohorts of this study depends only on the availability of subjects at the NIH Clinical Center.

12.2 PARTICIPATION OF CHILDREN

Children will not participate in this study for the reasons indicated in the eligibility criteria.

12.3 PARTICIPATION OF SUBJECTS UNABLE TO GIVE CONSENT

Adults unable to give consent are excluded from enrolling in the protocol. However, re-consent may be necessary and there is a possibility, though unlikely, that subjects could become decisionally impaired. For this reason and because there is a prospect of direct benefit from research participation (section 12.4.4), all subjects will be offered the opportunity to fill in their wishes for research and care, and assign a substitute decision maker on the "NIH Advance Directive for Health Care and Medical Research Participation" form so that another person can make decisions about their medical care in the event that they become incapacitated or cognitively impaired during the course of the study. Note: The PI or AI will contact the NIH Ability to Consent Assessment Team (ACAT) for evaluation as needed for the following: an independent assessment of whether an individual has the capacity to provide consent; assistance in identifying and assessing an appropriate surrogate when indicated; and/or an assessment of the capacity to appoint a surrogate. For those subjects that become incapacitated and do not have pre-determined substitute decision maker, the procedures described in NIH HRPP SOP 14E for appointing a surrogate decision maker for adult subjects who are (a) decisionally impaired, and (b) who do not have a legal guardian or durable power of attorney, will be followed.

12.4 EVALUATION OF BENEFITS AND RISKS/DISCOMFORTS

12.4.1 Risks

12.4.1.1 Study Drug

Potential risks of the study include the possible occurrence of any of a range of side effects as listed in section 13.1.3 and the consent document. The procedure for protecting against or minimizing risks will be to medically evaluate patients on a regular basis, provide premedications and supportive therapies as described earlier.

12.4.1.2 Research Blood Collection

Side effects of blood draws include pain and bruising, lightheadedness, and rarely, fainting.

12.4.2 Image Guided Biopsy Collection

The risks of the research biopsy collected at baseline include pain, bleeding and infection at the biopsy site. In addition, as the biopsy may be collected under CT guidance, subjects in this study may be exposed to approximately 0.80 rem. This amount is below the guideline of 5 rem per year allowed for adult research subjects by the NIH Radiation Safety Committee.

12.4.3 Non-Physical Risks of Genetic Research

These risks are noted in the consent document.

12.4.4 Benefits

The potential benefit to a patient (including those who have lost the capacity to consent) participating in the study is a reduction in the bulk of his/her tumor, which may or may not have a favorable impact on symptoms and/or survival.

12.5 RISK BENEFIT ASSESSMENT

Patients with advanced and/or metastatic mesothelioma, are in continuous need of improved therapy options. This is especially true for patients who have progressed on standard therapy such as the patient population that will be eligible for this trial. Pre-clinical and clinical data (see sections 1.2.2 and 1.2.3) suggest that olaparib may improve outcomes in patients with mesothelioma, particularly in those with mismatch repair defects. A number of clinically appropriate strategies to minimize risk to patients have been built into the protocol through the means of inclusion/exclusion criteria, monitoring strategies, and management guidelines. Overall, the potential benefits of olaparib for mesothelioma patients retaining the ability to consent and those who lose capacity to consent during the course of the trial outweigh the risks associated with the proposed entry-into-human trial with olaparib.

12.6 CONSENT PROCESS AND DOCUMENTATION

The procedures and tests involved in this study and the associated risks, discomforts and benefits of these processes including the disclosure of genetic results (see section 5.3.1), will be carefully explained to the patient, and a signed informed consent document will be obtained prior to entry onto the study.

12.6.1 Telephone Re-consent

Reconsent by telephone is permitted on this study. Telephone consent will be obtained per OHSRP/IRBO and CCR policies and procedures..

13 PHARMACEUTICAL INFORMATION

There will be no IND obtained for the use of the commercial agent (olaparib) used in this study.

This study meets the criteria for exemption for an IND as this investigation is not intended to support a new indication for use or any other significant change to the labeling; the drug is already approved and marketed and the investigation is not intended to support a significant change in advertising; and the investigation does not involve a route of administration or dosage level in use in a patient population or other factor that significantly increases the risks (or decreases the acceptability of the risks) associated with the use of the drug product.

13.1 OLAPARIB)

13.1.1 Source

The olaparib tablets used in this study will be supplied under a collaborative agreement with the manufacturer, AstraZeneca.

13.1.2 Mode of Action:

Olaparib is an inhibitor of subclasses 1, 2, and 3 of polyadenosine 5' diphosphoribose polymerase (PARP-1, PARP-2, and PARP-3). In tumors that are deficient in the homologous recombination DNA repair pathway (example, BRCA mutants), inhibition of PARP by olaparib causes accumulation of DNA double-strand breaks and genomic instability. Olaparib may also enhance the effects of DNA damage caused by ionizing radiation and chemotherapy.

